## 4.4 Strategies for Recruitment and Retention

Before the study is initiated, it will be approved by the Institutional Review Board (IRB) at each treatment site and the Network DSMB. All of the subjects and their parent/guardian will provide consent/assent for participation in this study. In addition to the informed consent requirements, per the Privacy Rule (HIPAA) regulations, research participants will provide a written "authorization" to use their Protected Health Information (PHI) in connection with research. In requesting an authorization from potential participants, investigators will specify how the information will be used and how the privacy of that information will be protected. The researcher obtaining Informed Consent will thoroughly review the consent form with the child and his or her parents, including study procedures and potential risks and benefits of study participation. The child and parents will be encouraged to ask questions throughout the process. It will be emphasized that research is voluntary and that the subject can opt out of this project at any time without jeopardizing his/her treatment. Participants who turn 18 during their participation in the study and who have the cognitive capacity to read and understand the consent form, and whose parents do not have legal guardianship of them, while participating in this study will be re-approached by one of the physician investigators. The investigator will continue the informed consent process acknowledging that the individual is now legally an adult and will ask the participant if they voluntarily wish to continue their participation in the study. If he/she does, the participant will be asked to sign the informed consent document and a new HIPAA authorization. If the individual does not wish to continue participation they will be withdrawn from study treatment just as any other individual who chooses to withdraw consent from participation.

This study will be registered in ClinicalTrials.gov no later than 21 days after the first subject is enrolled. Summary results information (including adverse events) will be reported no later than 1 year after the completion date for the study. Grant and progress report forms shall include a certification that the investigators have made all required submissions to ClinicalTrials.gov.

Randomization Method: We will randomize centrally, using our data management system. The UNC Data Team is familiar with this process as they have done this in our multicenter IMPACT trial. When a site needs to randomize a subject, after baseline is assessed, the coordinator opens the Randomization form. This form uses already assessed strata to randomize from the appropriate stratum. We will not stratify by site. We felt that both functional status and age group were more likely to be related to the outcome than site, and there are limits to how many strata we can have. We will stratify by functional status (high or low) and age group (3 age groups), producing 6 strata. The unblinded statistician will generate a randomization plan for each of the 6 strata, using a permuted block algorithm with randomly selected block sizes of 2 and 4, using SAS. The table will be exported to an Excel file and sent to the data manager. This can be done without having the lead statistician ever actually see the randomization plan. (He/she will debug the program and when debugged, run it with a new seed for the random number generator without seeing the results.) The database manager will import the randomization plan as a table in Access. The Randomization form

will use Visual Basic code and the values of the strata variables to enter the correct subset of the table and choose the first unused treatment. It will generate an ID number and send an email to the appropriate pharmacy, where drug will be assigned.

## 4.5.2 Masking Procedures

The spray and a matched placebo solution containing all of the same ingredients except for oxytocin will be packaged in indistinguishable nasal administration bottles.

#### 5 STUDY INTERVENTION/INVESTIGATIONAL PRODUCT

## **5.1 Study Product Description**

Oxytocin contains the synthesized peptide oxytocin in a solution formulated to promote absorption through the nasal mucosa.

## 5.1.1 Acquisition

All the proper documentation regarding how the drug and placebo is compounded/manufactured will be submitted to the FDA as an amendment to the current IND (#111604) held by [name] for sustained intranasal oxytocin treatment in 3-17 year olds with autism.

## 5.2 Dosage, Preparation and Administration of Study Intervention/Investigational Product

Participants in the study will be randomly assigned to treatment with intranasal oxytocin or placebo. Participants or their caregivers will be taught to administer the nasal spray, alternating nostrils, by the study personnel. The caregivers will be provided with suggestions for how to encourage their children to comply with the procedure including setting up a fun routine and providing rewards. The caregivers will also be provided with a dosing handout to monitor subjects' weekly dosing to ensure that participants are reaching their optimal dose. The study staff will fill in the dates at each visit and the dosing (if applicable). **The target dose for the study is 48/0 IU total daily dose (TDD).** The target dose will begin at the week 8/28 visit, unless issues with tolerance or compliance slow the recommended titration schedule. **Every effort will be made to achieve the target dose of 48/0 IU TDD** unless it is clear that the child cannot tolerate it.

## 5.2.1 Flexible Dose:

In the blinded phase, dosing will be flexible between 8/0 IU TDD and, after the target dose (48 IU TDD) has been maintained for  $\sim 7-8$  weeks, up to 80/0 IU TDD, to allow one to optimize dosing for the individual child in cases of intolerance or inadequate response. Doses will typically be given in two equal amounts in the AM and the PM, with the maximal dose at any one time being 48/0 IU. If doses are uneven the larger dose should be given in the AM.

In the open label phase, dosing will be flexible between 24 IU TDD and, after the target dose (48 IU TDD) has been maintained for  $\sim$ 7-8 weeks, the dose can be increased to 72 TDD at week 36. The

preferences is for 24 IU TDD to be given in the AM, 48 IU TDD should be split equally between morning and PM dosing and 72 IU TDD should be split as 48 IU in the AM and 24 IU in the PM.

## **Suggested Titration to the Target Dose**

Blinded Phase: In the double-blind phase, titration to the target dose is expected to take 8 weeks and follow the suggested table below unless there are issues with tolerance or compliance. Dosing will begin at 8/0 IU in the AM at baseline. Typically, the dose will increase to 8/0 IU twice daily (BID) (16/0 IU TDD) at week 2. Dose will then be increased by 8/0 IU twice daily (BID) at weeks 4 and 8 with TDDs of 32/0 IU and 48/0 IU respectively. During the initial titration period (baseline to week 8), dosing increases should never occur before the time point specified in the schedule. Specifically one could not go to a TDD of 16/0 IU prior to week 2, or 32/0 IU prior to week 4 or 48/0 IU prior to week 8.

Week 0	Week 2	Week 4	Week 8
8 IU qD	8 IU BID	16 IU BID	24 IU BID
(8 IU TDD)	(16 IU TDD)	(32 IU TDD)	(48 IU TDD)

**Open Label Phase:** In the open-label phase, from week 24 to week 28, the dose will be 24IU in AM for a TDD of 24 IU. From week 28-36 the dose will be 48 IU TDD (ie. 24 IU BID). At week 36 the dose can be increased to 72 IU TDD (ie. 48 IU in the morning and 24 IU in the afternoon).

Week 24	Week 28
24 IU qAM	24 IU BID
(24 IU TDD)	(48 IU TDD)

#### **5.2.3** Dose Deviations from Titration Schedule

#### Maintaining pre-target dose:

In the blinded phase (week 0-24) If the child is having difficulty tolerating the medication or administration of the nasal spray during the initial dose titration phase, the clinician may choose to hold the dose at weeks 2, 4 or 8 rather than increasing per the titration suggestions. If dose is held, it may then be increased by 8/0 IU 1-2 x/day after assessment of the participant (phone/email or in person) between scheduled visits if desired in order to achieve the target dose of 24/0 IU twice daily or 48/0 IU total daily dose as close to the week 8 visit as possible.

In the open-label phase if the child is having difficulty tolerating the medication, the clinician may choose to hold the dose at 24 IU qD at week 28, 32, 36, 40, or 44.

**Dosing Reductions:** All dosing reductions should be discussed with the site PI within 2 business days and reported to the lead site for discussion with other treatment site PIs.

**Mandatory Dose Reductions**: The dose must be reduced to the highest previously well tolerated dose *if any of the following criteria* are met AND the treating clinician is

comfortable with the decrease. The dose may be reduced between appointments in the first two cases.

Clinician judges an AE to require immediate reduction of dose OR CGI-I score is 6 or 7 OR

Two consecutive CGI-I scores at in person visits are worse than the preceding two CGI-I scores.

If any of the three criteria are met, but the treating clinician is not comfortable with the decrease, the dose will be maintained until discussed with the all treating site PIs. The majority of the treating site PIs may determine that a mandatory decrease should be made.

## **Optional Dose Reductions:**

In the blinded phase the dose may be reduced by 8/0 IU once or twice a day at any time at the clinician's discretion due to a clinically significant adverse event, poor tolerability of dosing, parent request. The dose should not be subsequently increased without reassessing the participant by phone/email or in person. The dose can be increased between scheduled visits after clinical reassessment of the participant (phone, email or in person). SLAES and CGI-I to be completed at physician discretion. If SLAES is not completed, then adverse events must be assessed and documented.

In the open-label phase the dose may be reduced in 24 IU increments to a minimum dose of 24 IU every other day.

## **Dosing Increases Above Target Dose:**

In the blinded phase after the target dose has been maintained for at least 7 weeks the dose may be increased by 16/0 IU TDD only at each of the subsequent visits. Thus, at week 16, the maximal possible dose will be 64/0 IU TDD. However, at week 20 the dose could be increased to either 64/0 IU TDD if there had been no prior increase at week 16 or, could be increased to 80/0 IU TDD if the dose had been increased at week 16.

In the open-label phase after the target dose has been maintained for  $\sim$  7-8 weeks then the dose can be increased (at week 36) to 72 IU TDD.

**Applies to both phases:** Increases past the target dose are NOT required and may ONLY be made if the following conditions are met

- No evidence of clinically significant adverse events
- Parents agree
- Clinician agrees

## **5.2.4** Weaning Dose at Completion of Trial

For 72 IU TDD at week 48 we would reduce dose to 24 IU BID for 1 week then 24 qAM and then 24 IU every other day in the morning for a week then stop.

For 48 IU TDD at week 48 we would reduce to 24 IU every morning for a week and then reduce to 24 IU every other day for 1 week then stop.

For 24 IU TDD at week 48 we would reduce to 24 IU every other day for 1 week then stop. For anything less than 24 IU TDD, no down titration is required

For early terminations, attempts should be made to follow down titration as listed above. It will not be considered a deviation if families are non-compliant.

#### At week 53-55 a phone/email visit should be completed to review the SLAES.

## 5.2.5 Interrupting Dosing

Administration of oxytocin may be interrupted on rare occasions due to other clinical conditions that temporarily prevent nasal administration, poor compliance with administration directions, or significant adverse events or acute worsening of symptoms or functioning. The treating clinician may restart treatment at the same or a lower dose after assessment of the participant (including email/phone with participant's caregiver). The lead site should be informed of interrupted dosing lasting more than 1 week.

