## 5.5 Blinding/Unblinding

Due to the short half-life of oxytocin (estimated 3-15 minutes), and the lack of any treatment for overdose, unblinding will not be permitted in this study. The knowledge of treatment assignment will not alter the subject's immediate management, so therefore unblinding is not deemed appropriate for this study. Instead, in the case of a medical emergency, unexpected serious adverse reaction or clinician judgment, the study medication may be interrupted. Study medication may be interrupted (temporarily discontinued) at the discretion of any treating physician at a site at any time without prior approval from the site PI or Steering Committee (SC). In the case when the treatment is interrupted, the subject may be re-challenged if the case is discussed and approved by the SC.

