#### 6.6 Unscheduled Visit or Re-Evaluation Visit

Subjects may be asked to come in for an unscheduled visit at any time during the course of the study if the treating physician feels it is necessary to see the subject in person or to complete a PK visit. Subjects will be instructed to contact the site between scheduled visits if there are any issues that need to be addressed.

Subjects may also be re-evaluated with appropriate assessments completed for any of the following reasons:

- If the subject's dose is mandatorily reduced, then these assessments should be completed 2-4 weeks after the dose has been reduced.
- If the subject has had a CGI-I score of 6 or 7, then the assessments should be completed two-four weeks later at physician discretion.

During these visits, all efforts should be made to obtain the following assessments:

- Vital signs (only if in person visit)
- Review of concomitant medications
- SLAES (adverse events) and suicidality assessment
- CGI-S and CGI-I
- Focused Clinical Physical Exam (only if in person visit)
- If physician feels it is indicated, safety labs or ECG may be obtained.

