#### **Unscheduled Assessments**

If the site learns that a participant's treatment has been interrupted for 1 week or longer, an unscheduled visit should be performed.

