## **8.1.1** Treatment Emergent Adverse Events

In this trial we are documenting all AE's, but analysis will focus only on Treatment Emergent AE's (TEAE's). Medical and behavioral conditions that are present at screening and/or baseline will only be considered treatment emergent adverse events if their severity increases significantly after the participant has taken at least one dose of study treatment. Intermittent conditions such as seasonal allergies will only be considered TEAEs, if the severity or frequency is significantly greater than in the previous two years. Only TEAEs will be considered in the adverse event safety analyses.

If a TEAE occurs, its relationship to study product (assessed only by those with the training and authority to make a diagnosis, which would include MD, DDS, DMD, PA, Nurse, Nurse Practitioner or DO), and resolution/stabilization will be coded at the resolution of the event or end of the subject's participation in the study. All TEAEs occurring while on study must be documented appropriately regardless of relationship. All TEAEs will be followed to adequate resolution. If a TEAE is a severe adverse event rating (3) and an Unexpected Problem (UP-no prior history of issue/not commonly seen in autistic patients and not described as a risk of the treatment), the UP form must be completed. If a TEAE is an SAE the the SAE form and SLAES (unscheduled visit) must be completed.

**Severity of Event:** All AEs will be assessed by the clinician using a protocol defined grading system. For events not included in the protocol defined grading system, the following guidelines will be used to quantify intensity.

- **Mild:** events require minimal or no treatment and do not interfere with the subject's daily activities.
- **Moderate:** events result in a low level of inconvenience or concern with the therapeutic measures. Moderate events may cause some interference with functioning.
- **Severe:** events interrupt a subject's usual daily activity and may require systemic drug therapy or other treatment. Severe events are usually incapacitating.
- Life-threatening: Substantial risk dying or requires intervention to prevent death
- Death related to AE: Subject died as a result of the event, self-explanatory

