#### **8.3 Reporting Procedures**

# 8.3.1 Treatment Sites Reporting to Duke

Any event that is considered reportable based on section 8.2 by the PI or Subinvestigator or which meets the aforementioned criteria must be submitted to the Coordinating Center. It should be reported on the following numbers. It is preferable to have a written report (fax or email) for documentation purposes.

Coordinating Center E-mail: [contact] and [contact]

The study clinician will complete and submit the appropriate reporting form within the following timelines:

 SAEs that are deaths and immediately life-threatening events, whether related or unrelated, will be recorded on the Serious Adverse Event Form and sent by fax within 2 business days of site awareness.

- SAEs other than death and immediately life-threatening events, regardless of relationship, will be reported by fax within 7 business days of site awareness.
- UPs Form within 7 business days of the site's awareness of the event.
- Pregnancies within 7 business days of the site's awareness
- Serious Suicidal Ideation within 7 business days of the site's awareness
- Alert lab or ECG values within 7 business days of the site's awareness
- Decisions to reduce dose within 7 business days.
- Interrupted dosing lasting more than 7 days within 7 business days of site's awareness.
- Requests to delay mandatory reductions in dose within 5 business days.
- Participants with a CGI-I of 6 or 7 within 7 business days of the assessment.

Other supporting documentation of the event may be requested and should be provided as soon as possible. Sites should report SAEs, UPs and other reportable events to their local IRB's per the local IRB's guidelines and procedures. This may differ between sites.

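### Protocol v6.0 gives two rules for resuming interrupted study drug (treating clinician in 5.2.5, Steering Committee approval in 5.5) and does not say which governs after a medical emergency or unexpected serious reaction

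*Combined protocol and SAP*

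**What the plan says.** **Section 5.2.5 (Interrupting Dosing)** expects interruptions to be rare and gives four reasons: a condition that prevents nasal dosing, poor compliance, significant adverse events, and acute worsening. For all four, "The treating clinician may restart treatment at the same or a lower dose after assessment of the participant". The assessment may be by phone or email with the caregiver. The lead site is to be told only if the gap exceeds one week.

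**Section 5.5 (Blinding/Unblinding)** does not permit unblinding. In its place, "in the case of a medical emergency, unexpected serious adverse reaction or clinician judgment, the study medication may be interrupted". Study drug "may be interrupted (temporarily discontinued) at the discretion of any treating physician at a site at any time without prior approval"; neither the site PI nor the SC has to agree first. The section then sets the condition for resuming: "In the case when the treatment is interrupted, the subject may be re-challenged if the case is discussed and approved by the SC".

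**Other provisions that touch an interruption:**
- Section 8.1.1: "If a TEAE is an SAE the the SAE form and SLAES (unscheduled visit) must be completed".
- Unscheduled Assessments: where a participant's "treatment has been interrupted for 1 week or longer, an unscheduled visit should be performed". Section 6.6 gives the content of such a visit and allows it to be remote.
- Section 8.3.1 lists among the sites' reporting duties: "Interrupted dosing lasting more than 7 days within 7 business days" of the site becoming aware.

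**The concern.** A child whose drug is stopped after an unexpected serious reaction can be placed under either section. Under 5.2.5 the treating clinician may resume dosing after a phone call. Under 5.5 the SC must first discuss and approve the case. Neither section cites the other, so two sites facing the same event could act differently and each could point to the protocol.

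What is at stake is re-exposure of a child aged 3 to 17 without the check that 5.5 describes. In weeks 0 to 24 that decision is also made without knowing the assignment, because 5.5 offers interruption in place of unblinding.

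**Working it through.** No arithmetic underlies the two rules, so the check sets the current v6.0 texts side by side and then asks whether anything else settles the question.

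**Step 1. The two rules.**

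| | 5.2.5 | 5.5 |
|---|---|---|
| Reasons for interruption | Nasal dosing prevented; poor compliance; significant adverse events; acute worsening | Medical emergency; unexpected serious adverse reaction; clinician judgment |
| Who decides on resuming | Treating clinician | SC, by discussion and approval |
| Basis | Assessment, which may be remote | SC review of the case |
| Wait before resuming | None stated | Until approval; no turnaround stated |
| Reference to the other section | None | None |

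**Step 2. Overlap.** An unexpected serious adverse reaction is naturally also a significant adverse event, and acute worsening may be a medical emergency. On a narrow reading of 5.5 (emergencies and unexpected serious reactions only), up to 2 of the 4 reasons in 5.2.5 therefore also fall under 5.5. Clinician judgment could cover any interruption, and the re-challenge sentence is not limited by reason. On the widest reading all 4 of 4 overlap.

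**Step 3. Does another provision settle it?** None names who authorises the first resumed dose.
- 8.1.1 requires the SAE form and an adverse-event visit, but does not place them before the restart.
- The unscheduled visit applies only from one week. The interruption notices in 5.2.5 and 8.3.1 apply only beyond one week or 7 days. A shorter gap triggers none of these.
- 5.2.3 requires dose reductions to be discussed with the site PI within 2 business days. A restart at a lower dose may engage this, but it is not SC approval.
- 8.5 requires SC and medical monitor agreement to continue when CGI-I stays at 6 or 7. The trigger is the score, not the interruption.
- 8.5 also requires withdrawal if the medical monitor thinks that worsening or a life-threatening event is likely to be treatment-related. That depends on the monitor having formed a view.

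**Step 4. Can reporting stand in for approval?** The inputs are the limits in 8.3.1 (site to coordinating center: 2 business days for deaths and immediately life-threatening events, 7 for other SAEs) and 8.3.2 (coordinating center to SC: 14 business days). With each limit used in full, the latest first notice to the SC is:
- immediately life-threatening event: 2 + 14 = 16 business days after site awareness;
- other SAE: 7 + 14 = 21 business days.

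The medical monitor is informed by the coordinating center within 14 days (8.3.2) and reviews within 14 working days (8.6.1). Since 5.2.5 states no minimum wait, dosing could resume before the SC or the monitor has seen the case, with every deadline met.

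**The case against.** The best counter-argument is that the sections can be read together. Section 5.2.5 sits with the dosing rules and covers gaps in general. The text in 5.5 replaces emergency unblinding. One speaks of *restarting*, the other of *re-challenge*. The permission in 5.2.5 does not exclude a further approval, so a site could assess the child and, in a 5.5 case, also wait for the SC. *Serious* is defined in 8.2.1, while *significant* in 5.2.5 is not, so it is an inference that 5.2.5 was meant to reach serious reactions.

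This reading is sensible and probably close to what was intended, but the protocol does not state it. Neither *restart* nor *re-challenge* is defined, 5.2.5 is not confined to non-serious events, and 5.5 includes clinician judgment.

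Other parts of the objection stand and limit the point:
- A reader might infer that the SC is left unaware. It is not: 8.3.2 sends SAEs, unanticipated problems and other reportable events to the SC and the medical monitor. That is notice after the event, not permission.
- A reader might infer that every restart decision is blind. Only those in weeks 0 to 24 are; from week 24 all children receive open-label oxytocin, and 5.2.5 covers both phases.
- Section 5.5 gives its reason for not unblinding: knowing the assignment would not alter the child's immediate management. The point here is not a criticism of that choice.

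**Conclusion.** The inconsistency is real in the current text and worth correcting, but it is minor. It concerns participant safety and uniform site conduct. It has no bearing on the estimand, alpha, power or any planned analysis.

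Its frequency is unknown. Section 5.2.5 expects interruptions on few occasions, the documents give no count, and those following an emergency or unexpected serious reaction are a subset. The overlap of 2 to 4 listed reasons counts phrases; a reader might take it as a measure of risk or of children affected, and it is neither. Nor do the documents show that any site resumed drug without SC approval.

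The conclusion rests on one assumption: that a serious reaction counts as a significant adverse event under 5.2.5. If the sponsor intended otherwise, the remedy is still to say so.

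**What to change.** State in 5.2.5, with a matching cross-reference in 5.5:

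> After an interruption for a medical emergency or an unexpected serious adverse reaction, study drug is not resumed until the SC has discussed and approved re-challenge (5.5). After every other interruption, including one made on clinician judgment alone, the treating clinician may restart after assessing the child (5.2.5).

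The request should go through the coordinating center, the existing route for reportable events, with an expedited SC turnaround set by the sponsor. The hold should not extend to all SAEs regardless of relationship.

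The drafting cost is wording in two sections and a site memo. The real cost is a dosing gap for a few children. No SC turnaround for re-challenge is stated; the nearest clock is the 10 business days in 8.5, which is two calendar weeks at 5 business days per week. A hold that reaches one week brings in the unscheduled visit. The per-protocol definition in SAP v2.0, 2.1.3, accepts at least 22 of the 24 weeks on drug with 80% compliance, an allowance of 24 − 22 = 2 weeks. If held time counts as time off drug, which the SAP does not say, a two-week hold would use all of it and a longer one could remove the child from that set. The set is used only for supportive analysis, but this is a reason to keep the turnaround short.
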